7.1.5. Serious Adverse Events

Serious adverse events (SAEs) will be identified and captured as SAEs if the AEs met the definitions of SAEs that were specified in the study protocol. SAEs captured and stored in the clinical database will be reconciled with SAEs on the Gilead global safety database before data finalization.

7.1.6. Treatment-Emergent (TE) Adverse Events (AEs), Non-TEAEs, and AEs Through FU Week 24

7.1.6.1. Definition of TEAEs

TEAEs are defined as 1 or both of the following:

- Any AEs with an onset date on or after the start date of any study drug and on or before the composite last on-treatment date + 30 days after permanent discontinuation of study drug
- Any AEs leading to premature discontinuation of any study drug

7.1.6.2. Definition of Non-TEAEs

Non-TEAEs are defined as defined as any AEs with an onset date after the composite last on-treatment date + 30 days after permanent discontinuation of study drug through the end of the study.

7.1.6.3. Definition of AEs through FU Week 24

AEs through FU Week 24 are defined as any AEs with an onset date on or after the start date of any study drug and on or before the composite last on-treatment date + 24 weeks after permanent discontinuation of study drug.

Definitions of the composite last on-treatment date for each cohort can be found in Section 3.8.2.

7.1.6.4. Incomplete Dates

If the onset date of the AE is incomplete and the AE stop date is not prior to the first dosing date of any study drug, then the month and year (or year alone if month is not recorded) of onset determine whether an AE is treatment emergent.

The event is considered as TE if both of the following 2 criteria are met:

- The AE onset is the same as or after the month and year (or year) of the first dosing date of any study drug, and
- The AE onset date is the same as or before the month and year (or year) of the date corresponding to the cutoff day in Section 7.1.6.1.

The event is considered as non-TE if the AE onset date is after the month and year (or year) of the date corresponding to the cutoff day in Section 7.1.6.2.

The event is considered as AEs through FU Week 24 if both of the following 2 criteria are met:

- The AE onset is the same as or after the month and year (or year) of the first dosing date of any study drug, and
- The AE onset date is the same as or before the month and year (or year) of the date corresponding to the cutoff day in Section 7.1.6.3.

7.1.7. Summaries of Adverse Events and Deaths

7.1.7.1. Summaries of TEAEs

TEAEs will be summarized based on the Safety Analysis Set.

The analysis in this section regarding treatment-related TEAEs will be study drug specific (ie, SLGN, nivolumab, or VIR-2218) in the summaries.

A brief, high-level summary of the number and percentage of participants who experienced the following will be provided for each cohort: any TEAE, any TEAE of Grade 3 or above, any TEAE of Grade 2 or above, any treatment-related TEAE, any treatment-related TEAE of Grade 3 or above, any treatment-related TEAE of Grade 2 or above, any TE SAE, any treatment-related TE SAE, any potential immune-related AEs (irAEs), any potential uveitis, any AE leading to premature discontinuation of any study drug, any AE leading to temporary interruption of any study drug. All deaths (including those that are treatment-emergent and those that are not treatment-emergent) observed in the study will also be included in this summary. Within Cohort 2, the summary will be presented by treatment group (Group A or Group B).

Adverse event summaries with the number and percentage of participants who experienced at least 1 TEAE will be provided and summarized by SOC and PT for each cohort, and within Cohort 2, the summary will be presented by treatment group (Group A or Group B), as follows:

- TEAEs
- TEAEs with Grade 3 or higher
- TE treatment-related AEs
- TE treatment-related AEs with Grade 3 or higher
- TE SAEs
- TE treatment-related SAEs
- TEAEs leading to premature discontinuation of any study drug
- TEAEs leading to temporary interruption of any study drug

Multiple events will be counted only once per participant in each summary. Adverse events will be summarized and listed first in alphabetic order of SOC, and then by PT in descending order of total frequency within each SOC.

A summary by SOC and PT by severity grade will be provided for TEAEs, TEAEs with Grade 3 or higher, and TEAEs related to study drug(s), and the most severe grade will be used for those TEAEs that occurred more than once in an individual participant during the study.

TEAEs, TEAEs with Grade 3 or higher, TEAEs with Grade 2 or higher, TE SAEs, TE treatment-related AEs, TE treatment-related AEs with Grade 3 or higher, TE treatment-related AEs with Grade 2 or higher, and TE treatment-related SAEs will be summarized by PT only, in descending order of total frequency.

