1.2. Study Design

Approximately 40 NUC-suppressed and 60 viremic CHB-infected participants may be enrolled and assigned into a cohort below. Each cohort will enroll a minimum of 20% of HBeAg-positive participants, and up to 20% of participants can have HBsAg \leq 100 IU/mL.

NUC-suppressed Cohort

Cohort 1 (n = 40):

- TAF 25-mg tablet administered orally once daily for 36 weeks
- VIR-2218 200 mg administered via SC injection once every 4 weeks for 24 weeks (total 6 doses)

At Week 12, add-on and initiate the below treatment:

- SLGN 3 mg (2 × 1.5-mg tablets) administered orally while fasting once a week on the same day for 24 weeks (total 24 doses)
- Nivolumab 0.3 mg/kg administered IV once every 4 weeks for up to 24 weeks (up to 6 doses)

Viremic Cohort

Cohort 2 (n = 60)

Participants will be randomized 2:1 into Cohort 2 (Groups A and B) and stratified by HBsAg > or \leq 3 log₁₀ IU/mL.

Group A (n = 40):

• VIR-2218 200 mg administered via SC injection once every 4 weeks for 24 weeks (total 6 doses)

At Week 12, add-on and initiate the below treatment:

- SLGN 3 mg (2 × 1.5-mg tablets) administered orally while fasting once a week on the same day for 24 weeks (total 24 doses)
- Nivolumab 0.3 mg/kg administered IV once every 4 weeks for up to 24 weeks (up to 6 doses)

[figure not shown]
Group B (n = 20):

- SLGN 3 mg (2×1.5 -mg tablets) administered orally while fasting once a week on the same day for up to 24 weeks (up to 24 doses)
- Nivolumab 0.3 mg/kg administered IV once every 4 weeks for up to 24 weeks (up to 6 doses)

After completing study treatments all participants will enter the FU period.

Figure 1-1 provides the study design schema.

Figure 1-1. Study Design Schema*

IV = intravenous; NUC = nucleos(t)ide(s); PO = oral; Q4W = every 4 weeks; QD = once daily; QW = every week; SLGN = selgantolimod; SC = subcutaneous; TAF = tenofovir alafenamide

- a Viremic participants who meet criteria to initiate NUC treatment will receive TAF 25 mg once daily for up to 36 weeks during the study.
- b SLGN dosed while fasting once a week, on the same day, for 24 weeks.
- c Participants will continue to receive TAF per Protocol Section 3.5.
- * NOTE: Nivolumab dosing was stopped in this study and all treatments in Cohort 2 Group B were discontinued. This was a sponsor decision based on a benefit risk assessment on the use of nivolumab in HBV cure. Rationale is provided in Protocol Section 1.3.1.

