1.2.1. Changes to Study Design

Nivolumab dosing was stopped by Gilead as part of benefit-risk assessment based on emerging safety data from this study, other studies evaluating anti-PD-1/PD-L1 mAbs, and pertinent patient and prescriber insights {Cohen C. 2020}. As the study had completed enrollment and all participants were undergoing study treatment when the decision was made to stop nivolumab administration, the following measures were implemented:

- Stopped further nivolumab administration for all study participants across all cohorts
- Continued treatment with VIR-2218 and SLGN through Week 36 for Cohort 1 and Cohort 2 Group A
- Discontinued all study treatment for Cohort 2 Group B participants
- Stopped all sample collections related to nivolumab
- NUC treatment cessation was no longer required for NUC treated participants (Cohort 1)

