3.1.4. Safety Analysis Set

The Safety Analysis Set includes all participants who received at least 1 dose of study drug. This is the primary analysis set for safety analyses.

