4. PARTICIPANT DISPOSITION

4.1. Participant Enrollment and Disposition

Key study dates (ie, first participant screened, first participant enrolled, last participant last visit for the primary endpoint, and last participant last visit for the clinical study report) will be provided.

A summary of participant enrollment will be provided by cohort for each country or region, investigator within a country or region, and study overall. Within Cohort 2, the summary will be presented by treatment group (Group A or Group B) and stratification group (HBsAg \geq 3 or HBsAg \leq 3 log₁₀ IU/mL). The summary will present the number and percentage of participants enrolled/randomized. For each column, the denominator for the percentage calculation will be the total number of participants analyzed for that column. For Cohort 2, if there are discrepancies in the value used for stratification assignment between the IXRS and the clinical database, the value collected in the clinical database will be used for the summary. A listing of participants with discrepancies in the value used for stratification assignment between the IXRS and the clinical database at the time of data finalization will be provided.

The randomization schedule used for Cohort 2 will be provided as an appendix to the CSR.

A summary of participant disposition will be provided by cohort and study overall. Within Cohort 2, the summary will be presented by treatment group (Group A or Group B) and stratification group (HBsAg \geq 3 or HBsAg \leq 3 log₁₀ IU/mL). This summary will present the number of participants screened, the number of participants who met all eligibility criteria but were not enrolled/randomized with reasons participants not enrolled/randomized, and the number of participants in each of the categories listed below:

- All Enrolled Analysis Set
- All Randomized Analysis Set
- Full Analysis Set
- Safety Analysis Set
- FU Analysis Set
- SLGN PK Analysis Set
- SLGN PK Substudy Analysis Set
- SLGN completion status
 - Completed SLGN
 - Prematurely discontinued SLGN

- Reasons for premature discontinuation of SLGN
- Nivolumab completion status
 - Nivolumab not initiated
 - Completed nivolumab
 - Prematurely discontinued nivolumab
- Reasons for premature discontinuation of nivolumab
- VIR-2218 completion status
 - Completed VIR-2218
 - Prematurely discontinued VIR-2218
- Reasons for premature discontinuation of VIR-2218
- TAF completion status (for Cohort 1 during treatment phase only)

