4.2.2.4. On-Treatment Adherence for Nivolumab

The level of on-treatment adherence to nivolumab will be determined by the total amount of study drug administered relative to the total amount of study drug expected to be administered during a participant's actual on-treatment period based on the study drug regimen.

The level of on-treatment adherence will be expressed as a percentage using the following formula:

Adherence (%)
$$= \left(\frac{\text{Total No. of Nivolumab Administered [1]}}{\text{Total No. of Nivolumab Expected to be Administered on Treatment [2]}}\right) \times 100$$

- [1] The total number of nivolumab administered to a participant will be determined by the number of doses administered based on the study drug administration CRF.
- [2] The total number of nivolumab expected to be administered on treatment is determined as follows:
- For participants who completed nivolumab, the number of nivolumab expected to be administered will be set to 6;
- b For participants who did not complete nivolumab, the number of nivolumab expected to be administered is determined by the last administration visit (for example, for a participant in Cohort 1 and Cohort 2 Group A, if the last administration visit is Week 16, the number of nivolumab expected to be administered will be 2; for a participant in Cohort 2 Group B, if the last administration visit is Week 16, the number of nivolumab expected to be administered will be 5).

For participants who never initiate nivolumab, adherence will not be calculated.

Descriptive statistics for the level of on-treatment adherence with the number and percentage of participants belonging to adherence categories (< 50%, 50% to < 75%, 75% to < 100%, 100%) will be provided by cohort (and by treatment group for Cohort 2) for the Safety Analysis Set.

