7.1.3. Relationship of Adverse Events to Study Drug

Related AEs are those for which the investigator selected "Related" in the eCRF in response to the question for the relatedness to each study treatment, ie, SLGN, TAF, nivolumab, or VIR-2218.

Relatedness will always default to the investigator's choice, not that of the medical monitor. Events for which the investigator did not record relationship to study drug will be considered related to study drug for summary purposes. However, by-participant data listings will show the relationship as missing.

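### Drug-specific related-AE percentages are based on everyone dosed with any study drug, so participants who never started nivolumab stay in the nivolumab-related denominator

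*SAP*

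**What the plan says.** - **Numerator.** Section 7.1.7.1 states: "The analysis in this section regarding treatment-related TEAEs will be study drug specific (ie, SLGN, nivolumab, or VIR-2218) in the summaries". This covers the high-level summary and the tables of related TEAEs and related SAEs.
- **Analysis set.** The same section states: "TEAEs will be summarized based on the Safety Analysis Set". Section 3.1.4 defines that set: "The Safety Analysis Set includes all participants who received at least 1 dose of study drug". It is not tied to any one drug.
- **Start of treatment.** For Cohort 1 and Group A, Section 1.2 gives VIR-2218 first (with TAF in Cohort 1) and then says "At Week 12, add-on and initiate the below treatment", listing SLGN and nivolumab. Group B has no such delay.
- **Nivolumab stop.** Section 1.2.1 lists among the measures taken: "Stopped further nivolumab administration for all study participants across all cohorts". Enrollment was complete and all participants were on treatment at the time. VIR-2218 and SLGN continued in Cohort 1 and Group A.
- **Non-initiators.** Section 4.1 has the disposition category "Nivolumab not initiated", with no counterpart for SLGN. Section 4.2.2.4 says: "For participants who never initiate nivolumab, adherence will not be calculated".
- **Unrecorded relationship.** Section 7.1.3 says: "Events for which the investigator did not record relationship to study drug will be considered related to study drug for summary purposes".

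**The concern.** A percentage of participants with a nivolumab-related event is naturally read as a rate among people who received nivolumab. As planned, its denominator also holds people who did not. A Cohort 1 or Group A participant who had not reached Week 12 when nivolumab was stopped could never receive it. That participant is in the Safety Analysis Set through VIR-2218 or TAF.

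The plan recognises this group in two places (disposition and adherence) but not in the related-AE tables. Section 1.2.1 attributes the stop to a benefit-risk assessment that drew partly on emerging safety data from this study. The nivolumab-related AE and SAE percentages are therefore among the results readers will look for, and adding unexposed people to the denominator makes them look lower.

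**Working it through.** **1. Confirm the staggered start from the plan's own figures.** Section 4.2.2.4 gives, for a last nivolumab administration at Week 16, 2 expected doses in Cohort 1 and Group A and 5 in Group B. Counting doses every 4 weeks:

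- Start at Week 12: Weeks 12 and 16, so 2 doses.
- Start at Day 1: Day 1 and Weeks 4, 8, 12 and 16, so 5 doses.

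Both figures reproduce. The delay is in Cohort 1 and Group A.

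**2. Check whether another rule removes the unexposed.**

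- Section 3.2 groups safety analyses by actual treatment, but treats it as different from the assigned treatment only if it differs over the whole treatment duration. No column exists for participants given VIR-2218 alone (with or without TAF), so they stay in their assigned column.
- Sections 7.1.1 to 7.1.7 contain no denominator limited to participants exposed to the drug in question.
- Section 4.2.2.4 also names the Safety Analysis Set, and it needs a separate sentence to drop never-initiators. Section 7.1.7.1 has no such sentence.

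**3. Size.** Let N be the Safety Analysis Set count in the column, k the number who never received nivolumab, and r the proportion with a nivolumab-related TEAE among the N − k exposed. If non-initiators contribute no related events:

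reported percentage = r × (N − k) / N; relative understatement = k / N.

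N = 40 is the planned size of Cohort 1 and of Group A (Section 1.2). The SAP gives neither k nor r, so both are assumptions here. With r = 25%:

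| k | Exposed | With related event | Reported (of 40) | Among exposed |
|---|---|---|---|---|
| 0 | 40 | 10 | 25.0% | 25.0% |
| 4 | 36 | 9 | 22.5% | 25.0% |
| 8 | 32 | 8 | 20.0% | 25.0% |
| 20 | 20 | 5 | 12.5% | 25.0% |

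With r = 50%, the reported figures at k = 0, 4, 8 and 20 are 50.0%, 45.0%, 40.0% and 25.0%.

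**4. The numerator.** TEAEs count from the first dose of any study drug (Section 7.1.6.1), and relatedness is asked for each treatment (Section 7.1.3). If the missing-is-related rule is applied drug by drug, a blank nivolumab item on an event before nivolumab, or in someone who never received it, would count as nivolumab-related. If m participants are counted for that reason alone, the reported percentage becomes [r × (N − k) + m] / N. With N = 40, k = 4, r = 25% and m = 1 (assumed), this is (9 + 1)/40 = 25.0%, which hides the dilution exactly. The two faults act in opposite directions, so both need fixing.

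**The case against.** **The denominator is not stated in words.** Section 7.1.7.1 names an analysis set, whereas Sections 4.1, 7.2.2.4 and 7.2.3 spell out their denominators. This does not rescue the plan. The ordinary reading of a percentage based on an analysis set is the count in that set, and Section 4.2.2.4 shows that the SAP states an exclusion when it wants one.

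**A reader can rescale.** Section 4.1 will report how many did not initiate nivolumab, and Section 4.2.1 will report doses administered, so the exposed number can be recovered by cohort and group. This stands as mitigation. It does not correct the percentages printed in the tables.

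**SLGN.** A reader might infer that SLGN-related rates are diluted as well. The mechanism is the same, but it needs participants who left before Week 12, and the SAP documents none. SLGN continued after the nivolumab stop.

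**Group A against Group B.** Since Group B starts without delay, a reader might infer a biased safety comparison. The SAP does not support that claim. It plans no between-group AE contrast: Section 3.5 rules out formal testing, and the difference estimates in Section 6.1.3 are for efficacy. The groups also differ in VIR-2218, in planned duration and in the stopping of all treatment in Group B, so an exposed-only denominator would not make them comparable.

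**Unrecorded relationship.** This point depends on reading Section 7.1.3 drug by drug and on a case report form that is not shown. It stands as an ambiguity to close.

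**Investigator attribution.** Dropping every event that began before a drug's first dose would override the investigator's entry, which Section 7.1.3 protects. That objection stands, and the fix below respects it.

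**Conclusion.** The point holds for nivolumab. Followed as written, the plan multiplies the nivolumab-related TEAE and SAE percentages in Cohort 1 and Group A by (N − k)/N whenever k participants never received the drug and none of them is counted as having a related event. The SAP provides for such participants but does not say how many there are, so the size cannot be fixed from the document. It is nil at k = 0 and, for an assumed 40 participants and an exposed rate of 25%, 2.5 points at k = 4 and 5.0 points at k = 8.

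It would go too far to say that the published rates will certainly be too low: k may be 0, and the missing-is-related rule could push the other way. All AE results are descriptive, so the consequence is a misleading percentage and not a wrong test. The change is worth making because it costs little and concerns the drug that was stopped.

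**What to change.** In Section 7.1.7.1:

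- For each drug-specific table or line of related TEAEs and related SAEs, take as denominator the Safety Analysis Set participants who received at least one dose of that drug. Alternatively, show that number and percentage beside the Safety Analysis Set figure.
- Keep the Safety Analysis Set for all-causality TEAEs.

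In Section 7.1.3:

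- Apply the missing-is-related rule only to drugs the participant had received by AE onset.
- Keep investigator-recorded attributions as entered, and query any entry of related that is dated before the first dose of that drug.

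**Cost.** SAP wording and some programming. First-dose dates per drug are already needed for exposure (Section 4.2.1), and the SLGN PK sets (Sections 3.1.6 and 3.1.7) already require a dose of the specific drug. Section 7.1.6.4 handles partial onset dates only against the first dose of any study drug, so the revised missing-relationship rule needs a matching convention for each drug. The downside is that denominators will differ between drug-specific tables, so each should print its own N.

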7.2.2.4. Summaries of Laboratory Abnormalities

Laboratory data that are categorical will be summarized using the number and percentage of participants in the study with the given response at baseline and each scheduled postbaseline visit.

The following summaries (number and percentage of participants) will be provided by lab test and cohort; within cohort 2, the summary will be presented by treatment group (Group A or Group B). Participants will be categorized according to the most severe postbaseline abnormality grade for a given lab test:

- Graded laboratory abnormalities
- Grade 3 or 4 laboratory abnormalities

For all summaries of laboratory abnormalities, the denominator is the number of participants with nonmissing postbaseline values.

The above summaries will be provided for 1) TE laboratory abnormalities, 2) non-TE laboratory abnormalities, and 3) laboratory abnormalities through FU W24.

By-participant listings of all laboratory abnormalities, and Grade 3 or 4 laboratory abnormalities will be provided by cohort, participant ID number and visit in chronological order. The listings will include all test results that were collected throughout the study for the lab test of interest, with all applicable severity grades or abnormal flags displayed.

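### Within Cohort 2, all-cause adverse events and worst-grade laboratory abnormalities are shown only as crude percentages over windows of unequal length: 282 planned days in Group A, at most 198 in Group B

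*SAP*

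**What the plan says.** SAP Section 7.1.6.1 counts an event as TE from the start of any study drug up to the "composite last on-treatment date + 30 days after permanent discontinuation of study drug". It also counts any event leading to premature discontinuation of a study drug. Section 7.1.6.3 replaces the 30 days with 24 weeks. Sections 7.2.2.1 and 7.2.2.3 use the same two cut-offs for laboratory abnormalities. Section 3.8.2 defines the composite date as the latest of the drug-specific last on-treatment dates.

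For adverse events, Section 7.1.7.1 gives participant counts: "Adverse event summaries with the number and percentage of participants who experienced at least 1 TEAE will be provided and summarized by SOC and PT". The columns within Cohort 2 are Groups A and B. For graded laboratory results, Section 7.2.2.4 says: "Participants will be categorized according to the most severe postbaseline abnormality grade for a given lab test". Potential immune-related events (Section 7.1.8) and liver-related abnormalities (Section 7.2.3) are likewise numbers and percentages of participants.

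Group A starts with VIR-2218 alone and then, per Section 1.2, "At Week 12, add-on and initiate the below treatment", namely SLGN and nivolumab. Group B starts both on Day 1, for up to 24 weeks. When nivolumab was stopped in all cohorts, Section 1.2.1 records for the other drugs: "Continued treatment with VIR-2218 and SLGN through Week 36 for Cohort 1 and Cohort 2 Group A". For Group B it records: "Discontinued all study treatment for Cohort 2 Group B participants".

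**The concern.** The percentage of participants with at least one event cannot fall as observation lengthens, and the chance that a worst-ever grade is high grows with the number of draws. Groups A and B are the study's only randomised contrast, and their safety columns stand side by side. If one column covers a longer period, a difference between them mixes the regimens with the length of observation. At equal underlying risk, Group A, the regimen with VIR-2218, would tend to show the higher percentage. Drug exposure is tabulated separately, drug by drug (Section 4.2.1). It is not expressed as time in the composite window, so a reader cannot turn the event percentages into rates.

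**Working it through.** The SAP states no window length in days, so the lengths are built from its own rules, with Study Day = 7 × week + 1.

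**Inputs.** Dosing comes from Section 1.2 and Appendix 1. Section 3.8.2 adds 27 days to the last VIR-2218 or nivolumab dose and 6 days to the last SLGN dose to give each drug's last on-treatment date.

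**Group A, as planned**
- VIR-2218: last dose Week 20 (Day 141); 141 + 27 = 168.
- SLGN: 24 weekly doses from Day 85, last on Day 246; 246 + 6 = 252.
- Nivolumab: last dose Week 32 (Day 225); 225 + 27 = 252.
- Composite date Day 252; TE window 252 + 30 = 282 days. It is still 282 without nivolumab, because SLGN alone gives Day 252.

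**Group B, planned maximum**
- SLGN: last dose Day 162; 162 + 6 = 168.
- Nivolumab: last dose Week 20 (Day 141); 141 + 27 = 168.
- Composite date Day 168; TE window 168 + 30 = 198 days.

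**Gap.** 282 − 198 = 84 days, and 84/282 = 29.8% of Group A's window. Through FU Week 24: 252 + 168 = 420 versus 168 + 168 = 336 days, the same 84 days (84/420 = 20.0%).

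**After the early stop.** The SAP gives no stop dates. If a Group B participant's last doses were at Week 16, 12, 8 or 4 (assumed), the window is 170, 142, 114 or 86 days.

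**Laboratory draws.** Table 3-1 has 10 scheduled postbaseline on-treatment visits for Group A; Table 3-6 has 7 for Group B. Counting FU Week 4 (FU Day 29) gives 11 versus 8, so 3 of 11 (27%) exist only in Group A. For participants who also had FU Week 2 (Table 3-10 footnote) it is 3 of 12 (25%).

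**Effect on percentages.** Assume the same constant daily hazard in both groups and full 282-day observation in Group A. Then p_B = 1 − (1 − p_A)^(d/282), where d is Group B's window in days. For example, 1 − 0.5^(198/282) = 38.5%.

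| Group A, 282 days | Group B, 198 days | Group B, 142 days (assumed stop) |
|---|---|---|
| 10% | 7.1% | 5.2% |
| 20% | 14.5% | 10.6% |
| 30% | 22.2% | 16.4% |
| 50% | 38.5% | 29.5% |
| 80% | 67.7% | 55.5% |

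The hazard that gives 50% at 282 days gives 64.4% at 420 days and 56.2% at 336 days in the tables through FU Week 24.

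**Time on SLGN and nivolumab.** From first dose of these drugs, Group A's planned window runs from Day 85 to Day 282: 282 − 85 + 1 = 198 days, equal to Group B's planned maximum.

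**The case against.** A reader might infer that Group B will look safer simply because it is watched for less time, and that the bias always runs that way. The SAP does not support that. Group B starts SLGN and nivolumab 12 weeks earlier than Group A, and nivolumab was stopped in every cohort during treatment. At the same time since enrolment, a Group A participant may have had up to 12 weeks less nivolumab, and Section 4.1 even has a category for never having started it. For harms of that drug the imbalance can run against Group B.

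Several displays are also largely outside the problem:
- Treatment-related events are reported by drug, and for SLGN and nivolumab the planned time at risk is 198 days in both groups. Only the early stops make those lines unequal.
- All deaths in the study are counted, and events leading to discontinuation count as TE whatever their onset date, so neither is bounded by the 30-day cut-off.
- Non-TE events run from that cut-off to the end of follow-up, a period of the same planned length in both groups.
- Numeric laboratory results, the ALT plot and categorical laboratory data are shown by visit (Sections 7.2.1 and 7.2.2.4), so Weeks 4 to 24 can be compared at the same time.

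Finally, safety is descriptive. Incidence over each regimen's own length is a legitimate description of that regimen, and one Group B participant in a planned 20 is already 5 percentage points.

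All of this stands, and it narrows the point to the all-cause and worst-grade lines. It does not remove it: those lines are unequal even as planned, and being descriptive is no protection when the descriptive percentage itself carries the distortion.

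**Conclusion.** The point holds for all-cause TEAEs, Grade 3 or higher TEAEs, TE SAEs, TE potential immune-related events and worst-grade TE laboratory abnormalities, and for their versions through FU Week 24. (Section 7.1.7.3 does not name its columns; I assume they follow Section 7.1.7.1.) The planned windows are 282 versus at most 198 days, and 420 versus at most 336. Both Group A figures are planned ones, and a participant who stops early has less.

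At equal, roughly constant hazard, Group B's percentages are pulled down. At 198 days the gap is 11.5 points where Group A shows 50% and 2.9 points where it shows 10%. It is larger if Group B's windows are shorter, and small if events cluster soon after first dose. These are illustrations of a tendency, not predictions of the observed tables. This is a weakness of presentation and interpretation. It does not affect the primary efficacy analysis or the validity of the trial.

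**What to change.** In Sections 7.1.7.1, 7.1.7.3, 7.1.8, 7.2.2.4 and 7.2.3, keep the crude percentages and add, by group:

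1. Total participant-time in the window and the exposure-adjusted incidence rate (participants with a first event per 100 participant-years at risk), for the all-cause overall, Grade 3 or higher and SAE lines and for Grade 3 or 4 laboratory abnormalities. For drug-related lines, start the time at risk at the first dose of that drug. Otherwise 84 of Group A's 282 days, before SLGN and nivolumab begin, would dilute its rates for those drugs.
2. For Cohort 2, cumulative incidence at a common time since first dose, censoring at the end of each participant's window. Choose the time from Group B's actual window lengths, before looking at events by group. Do not fix it at Day 198, where nobody in Group B may remain at risk.

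Add a table note that the crude Group A and Group B percentages cover different observation times.

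The cost is wording and a few extra columns from dates already collected. If the SAP is already final, Section 1 allows the change to be documented in the CSR. A rate assumes a roughly constant hazard, which the common-time estimate offsets. That estimate still compares groups that started SLGN and nivolumab 12 weeks apart, and the note should say so.
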